5.3. Potential Benefits

There are no direct benefits for the subjects who elect to enroll in this study. The results may provide identification and/or validation of new targets for the future development of therapeutics for subjects with atopic dermatitis, as well as increase current knowledge on the ability to transform the cutaneous microbiome, which could lead to potential therapeutic strategies for treating a variety of inflammatory skin conditions.

6. Investigational Agent /Device/Intervention

6.1. Investigational Agents/Devices/Interventions

6.1.1. Investigational Agent

6.1.1.1. Dosage, Preparation, and Administration

After isolation of each subject's antimicrobial *Staphylococcus* species from their skin swabs, a stock will be created that contains equal parts of each of these antimicrobial bacteria. This stock will be assigned a unique batch number, and the contents of this batch are what will be mixed with Cetaphil® at a

concentration between 1×10^5 and 1×10^8 CFU/gram Cetaphil® to create the subject's final AMT cream. This stock will be stored at -80C until the time when that subject's AMT cream is to be formulated. Prior to formulating the final AMT cream product that will be applied on the skin of that subject, though, this stock will undergo Microbial Limits Testing in accordance with USP <62>, as well as Microbial Limits Testing for the detection of *Streptococcus pyogenes*, *Acinetobacter baumannii*, and the skin fungus trichophyton in our laboratory both before and after formulation of the AMT cream with Cetaphil®.

The stock will be stored at -80C to prevent bacterial growth in the stock solution itself. If the stock is free from contaminants as shown by USP <62> testing, the stock will be formulated with Cetaphil® under sterile conditions in a sterile hood to prevent contamination. The stock will then be returned to -80C. If the stock is NOT free from contaminants as shown by USP <62> testing, the stock will be discarded appropriately. A sample of formulated AMT cream will then undergo UPS <62> tests for the organisms noted previously. Formulation of the subject's AMT cream will occur under sterile conditions in a sterile laminar flow hood to prevent contamination of the stock and AMT cream. A sample of Cetaphil® from each container of Cetaphil® used for the formulation of AMT cream will also undergo USP <62> testing within a week of using that Cetaphil® container for AMT cream formulation.

Bacterial concentration of the AMT cream will then be checked by plating a known quantity of the AMT cream on an agar plate and incubating the plate overnight at 37°C. The number of viable colonies will be counted the following day. Only AMT that has a final concentration of bacteria that ranges from 1×10^5 CFU of bacteria/ gram Cetaphil® to 1×10^8 CFU of bacteria/ gram Cetaphil® will be used in the clinical trial.

The AMT cream will be provided in single-dose sealed containers. The cream should be stored at room temperature per USP definition of "controlled room temperature" for up to one week. The AMT cream is meant to be applied topically two times a day at a dose of 3×10^7 CFU/ gram Cetaphil®.

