Preliminary work has identified an excellent vehicle for AMT. Clinical isolates of antimicrobial strains of *S. hominis* or known antimicrobial strains of *S. epidermidis* (ATCC12228) (12) were mixed with several different over-the-counter skin moisturizer creams at 1×10^7 CFU/gm. Cetaphil® Moisturizing Lotion (Galderma, TX) was found to be an excellent bacteriostatic vehicle. This formulation retained the viability of antimicrobial *Staphylococcus* for over 5 days at room temperature, but did not allow bacteria to grow (100% at day-2 and 50% at day-5). This formulation was active. A single topical application of this cream formulation containing a known antimicrobial strain of *S. epidermidis* (ATCC12228), or newly discovered antimicrobial strain of *S. hominis*, were found to successfully decrease *S. aureus* colonization on the skin of mice within 29 hrs in comparison to vehicle or similar formulations of known non-antimicrobial *S. epidermidis* strain (ATCC1457) (Fig.2). These data show that AMT on humans is likely to inhibit *S. aureus* colonization.

Clinical Studies

N/A

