1.4 Clinical Studies

In order to further examine if topical application of antimicrobial CoNS can decrease *S. aureus* survival on the skin of AD subjects, we conducted a preliminary double-blind, placebo-controlled autologous microbiome transplant study (AMT) under IND# 15786. An antimicrobial CoNS strain was isolated from the non-lesional

skin of each of 5 AD subjects who were *S. aureus* culture positive. To transiently increase their abundance on each subject, the active strains were expanded and then reapplied to the lesional forearm skin of the same subject, from which the active colonies were isolated, to a final concentration of 1×10^5 CFU/cm², a density similar to previous assessments of the abundance of bacteria on normal human skin. A single application of this functionally defined and autologously-derived CoNS strain(s) decreased *S. aureus* CFU within 24 hours; whereas, vehicle applied to the contralateral arm in a double-blind comparison did not (Fig. 4a-b). However, CoNS survival on the arm 24 hours after AMT was similar to the baseline. These results suggest that a single application of CoNS at a dose of 1×10^5 CFU/cm² was sufficient to transiently decrease survival of *S. aureus*, but the majority of transplanted CoNS died within 24 hours. Therefore, we propose to apply the AMT cream for multiple applications (BID for seven days) for better survival of transplanted CoNS.

[figure not shown]

Figure 4. Transplantation of antimicrobial CoNS reduces survival of *S. aureus* colonized on the skin surface.

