Intervention(s) and comparators: A coded cream consisting of Cetaphil® Moisturizing Lotion alone, or the microbiome transplant consisting of Cetaphil® Moisturizing Lotion plus 10^{5-8} CFU/gram Cetaphil® of coagulase negative *Staphylococci* clones expressing antimicrobial products isolated from the subject's own non-lesional skin. Since the two creams are indistinguishable in terms of color and texture, both the study coordinator and the subject will remain blinded to the identity of the cream. Our goal is to achieve a density of 1

$X 10^5$ CFU/10mg/cm² at the time of application. This abundance is known to be safe as it is the density of bacteria typically found on normal skin.

[Insert a schematic diagram of the trial here (include study cohorts and sample size, treatment allocation, time points of study intervention and subject follow-ups)]

Table format

Cohort	27 subjects	ARM 1	18 subjects: AMT cream
		ARM 2	9 subjects: Vehicle cream only

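### The cream's release floor of 10⁵ CFU/g lets through a batch that delivers 1% of the protocol's own target density on the skin

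*Combined protocol and SAP*

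**What the plan says.** Three statements about strength have to fit together.

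- **Goal on the skin.** Section 3.1 says "Our goal is to achieve a density of" 10⁵ CFU per 10 mg of cream per cm², to be met when the cream is applied. The same paragraph describes the cream as holding 10⁵ to 10⁸ CFU/g.
- **Stated dose.** Section 6.1.1.1 says "The AMT cream is meant to be applied topically two times a day at a dose of" 3×10⁷ CFU/g. It gives no tolerance around that figure and no conversion to CFU/cm².
- **Mixing and release limits.** Section 6.1.1.1 mixes the bacterial stock into the vehicle at 10⁵ to 10⁸ CFU/g. It then plates a sample ("The number of viable colonies will be counted the following day") and sets the acceptance rule: "Only AMT that has a final concentration of bacteria that ranges from" 10⁵ to 10⁸ CFU/g goes into the trial.

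The background sections give two reference points. Section 1.3 worked with cream at 10⁷ CFU/g and reports that formulation as active in mice. Section 1.4 reports that the five-subject pilot applied 10⁵ CFU/cm².

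**The concern.** A release limit should keep product that cannot deliver the intended dose out of the trial. Here the upper part of the range includes the concentration that the goal requires, but the lower limit bears no stated relation to the goal, the pilot density or the stated dose. No section explains how 10⁵ CFU/g was chosen. The number also appears in the goal, but there it is per cm² (per 10 mg of cream) and here it is per gram.

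Interpretation is what is at stake. Each AMT subject receives a separate batch grown from that subject's own strains, and only 18 AMT subjects are planned. If a few batches passed release at a small fraction of the intended strength, a null result could reflect either the concept or the dose.

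**Working it through.** **Inputs**

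- Goal: 10⁵ CFU/cm² at 10 mg = 0.010 g of cream per cm² (3.1).
- Release range: 10⁵ to 10⁸ CFU/g (6.1.1.1; same range in 3.1).
- Stated dose: 3×10⁷ CFU/g (6.1.1.1).
- Pilot density: 10⁵ CFU/cm² in one application (1.4).
- Viability in the vehicle at room temperature: 100% at day 2 and 50% at day 5, for test strains at 10⁷ CFU/g (1.3).

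**Concentration that the goal requires**

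Required CFU/g = goal ÷ film = 10⁵ ÷ 0.010 = 10⁷ CFU/g. This is the concentration used in 1.3, so the goal and the preclinical work agree.

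**Density that each permitted or stated concentration delivers**

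CFU/cm² = CFU/g × 0.010.

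| Cream (CFU/g) | Fresh (CFU/cm²) | Multiple of goal | At 50% viability (CFU/cm²) |
|---|---|---|---|
| 10⁵ (floor) | 10³ | 0.01 | 5×10² |
| 10⁶ | 10⁴ | 0.1 | 5×10³ |
| 10⁷ | 10⁵ | 1 | 5×10⁴ |
| 3×10⁷ (stated dose) | 3×10⁵ | 3 | 1.5×10⁵ |
| 10⁸ (ceiling) | 10⁶ | 10 | 5×10⁵ |

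Floor against goal and pilot density: 10⁵ ÷ 10³ = 100-fold short. Floor against stated dose: 3×10⁷ ÷ 10⁵ = 300-fold. On the log scale, two of the three decades in the release range (10⁵ to 10⁷) lie below what the goal needs.

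**Could the film thickness close the gap?**

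The application instructions in 8.3 call for a thin coat, one container per arm, and give no mg/cm². As an assumption, take films of 1 to 20 mg/cm². A floor batch then gives 10⁵ × 0.001 = 10² to 10⁵ × 0.020 = 2×10³ CFU/cm². To reach the goal from a floor batch would take 10⁵ ÷ 10⁵ = 1 g of cream per cm². At 3×10⁷ CFU/g it takes 10⁵ ÷ (3×10⁷) g = 3.3 mg/cm².

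**Does another control block a weak batch?**

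- The plate count is the only check on strength before use, and its acceptance range is the one at issue.
- Swabs are taken 5 minutes to an hour after the first application (8.3), when the subject has already been treated.
- Returned containers are weighed (6.4). That measures how much cream was used, not how many bacteria it held.

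These records would let the delivered dose be worked out afterwards. None of them stops a floor batch from being used.

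**The case against.** The strongest reply is that an acceptance limit is not a planned dose. Section 6.1.1.1 names 3×10⁷ CFU/g, and a batch made at that strength exceeds the goal threefold when fresh and by half at 50% viability. Section 3.1 calls its density a goal, not a specification. This stands as far as it goes: the documents do not suggest that batches will come out near the floor, and a reader should not infer that subjects will be under-dosed. It does not rescue the limit, because the wide range is also the stated mixing concentration and the stated dose has no tolerance that would exclude a batch at 10⁶ CFU/g.

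A reader might be tempted by several stronger claims.

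- **Storage makes the shortfall far worse.** Section 6.1.1.1 allows room-temperature storage for up to a week, and viability was 50% at day 5. But subjects receive fresh cream on Day 4 (3.1, 6.2, 8.3). At one container per arm twice daily, 18 containers less 2 spares last 16 ÷ 4 = 4 days, and 14 less 2 last 12 ÷ 4 = 3 days. Scheduled use therefore ends about 4 and then 3 days after dispensing. The age of the cream at dispensing is not given, and the Day 4 visit has a window of ±5 days, so some loss is possible. It is not the main evidence.
- **Repeat dosing cannot make up for a weak batch.** Section 1.4 says of the single pilot application "but the majority of transplanted CoNS died within 24 hours". That does not test cumulative dosing. Adding up doses also assumes no growth on the skin, whereas 1.3 shows absence of growth only in the cream.
- **The ceiling is unsafe.** Section 3.1 says of 10⁵ CFU/cm² "This abundance is known to be safe as it is the density of bacteria typically found on normal skin". That does not call higher densities unsafe, and the other safeguards (autologous strains, contaminant testing, halting rules) apply at any density.
- **Power is reduced.** Nothing in the documents links density to the size of the effect, so no loss of power can be calculated.

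**Conclusion.** The mismatch is real on the protocol's own figures. The lower limit admits cream at 1% of the concentration needed for the goal, 100-fold below the goal and pilot density on the skin and 300-fold below the stated dose. The conversion rests on the 10 mg/cm² in 3.1, and no film in the assumed range of 1 to 20 mg/cm² changes the conclusion for the floor.

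The threefold difference between the stated dose and the goal is a lesser matter. It may be an allowance for storage loss or for a thinner film, but no section says so; a sentence of explanation would settle it.

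This is a loose specification that should be corrected before batches are made. It is not evidence that the trial will fail or that any subject will be harmed. No minimum effective density is established, and sample size, alpha and power are not affected by this point.

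**What to change.** 1. In 6.1.1.1, and in the matching range in 3.1, raise the lower mixing and release limit from 10⁵ to 10⁷ CFU/g. Remake any batch that falls below it.
2. Keep 3×10⁷ CFU/g as the target, and state that it equals 3×10⁵ CFU/cm² at 10 mg/cm² when fresh. The new floor then sits 3×10⁷ ÷ 10⁷ = 3-fold below the target.
3. List each AMT subject's released batch CFU/g descriptively in the report.

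A batch exactly at the new floor meets the goal when fresh and would give 5×10⁴ CFU/cm², half the goal, at 50% viability. That is a twofold gap in place of the present 100-fold one.

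The cost is small: one changed limit, a sentence of conversion, and a listing built from plate counts already made and batch numbers already logged for each participant (6.3). The bacteria are expanded in vitro, so a stronger batch can be attempted. The downside is that a batch below 10⁷ CFU/g must be remade, which may delay that subject's treatment visit. The documents give no batch yields, so how often this would happen cannot be estimated.

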6.2. Study Design – dose schedule

The dosing schedule for the AMT cream or the Vehicle (Cetaphil® lotion) is described in Sections 8.3 and 8.5.

The first dose of the AMT cream or Vehicle cream will be administered to the subjects at the clinical site on Day 0 (Treatment Initiation Visit). At that time, they will be guided and given a handout instructing them to apply the AMT or Vehicle cream uniformly across both arms (this area will include *S. aureus* colonized lesions as well as non-lesional skin) twice daily for seven days. The participants will also be provided a subject diary and 18 single-use containers for dosing at home. An additional 14 single-use packets of AMT Product or Vehicle Product will be dispensed at the next clinic visit on Day 4 to use until Day 7. Subjects will be instructed that 2 additional single-use containers will be provided to them at Day 0 and Day 4 in the event that the subject should misplace a container of study cream. Accountability of the study creams will be performed, and subjects will be asked to return the jars of used and unused cream at the next in-clinic visit.

At the clinic visits on Day 4 and Day 7, the subjects will provide skin swab samples and be assessed for adverse events (AEs). Three additional clinic visits will be scheduled to assess safety and stability of the AMT cream. There will be a 30 day follow-up of all participants after the last treatment to assess safety and disease status. This will be brief phone call, and subjects will be asked to report any new adverse events and to answer questions regarding the status of their AD. Any subject with an ongoing AE/SAE at the time of this phone contact will continue to be followed until the event is resolved with or without sequelae.

6.3. Drug Accountability

Under Title 21 of the Code of Federal Regulations (21CFR §312.62) the investigator will maintain adequate records of the disposition of the investigational agent, including the date and quantity of the drug received, to whom the drug was dispensed (participant-by-participant accounting), and a detailed accounting of any drug accidentally or deliberately destroyed.

Records for receipt, storage, use, and disposition will be maintained by the study site. A drug-dispensing log will be kept current for each participant. This log will contain the identification of each participant and the date, quantity of drug dispensed, as well as the batch identifying number.

All records regarding the disposition of the investigational product will be available for inspection. Unused product will be destroyed as per UCSD's hazardous waste protocol.

6.4. Assessment of Participant Compliance with Investigational Agent

Patients will be required to return all aliquots of medications given, used or unused, and each vial will be weighed and weight recorded.

6.5. Toxicity Prevention and Management

All steps will be taken to minimize potential risks of the study. Patients will be excluded from study with known sensitivities/allergies to any of the products used during this study. Patients with any cracks or breaks in their skin, including severely excoriated or bleeding skin suggesting that the patient may be susceptible to an infection will be excluded. Similarly, subjects with prosthetic or implanted devices will also be excluded. Any adverse event, defined as any undesirable sign, symptom, or medical condition occurring after the subject's written consent to participate is completed, will be recorded and reported to the PI as well as the Institutional Review Board as required. If the PI believes an AE is possibly related to the study, the PI will determine whether or not it is in the best interest of the patient to continue in the study. To protect patient confidentiality, all samples will be encoded and anonymous. Strict adherence to current HIPPA guidelines will minimize the risk of loss of confidentiality. If the subject is injured as a result of participation in this research, treatment will be available. In the case of a skin infection, the subject would be treated according to standard treatment practices. The treatment will include antibiotics (for infection) and ointment (for irritation and dryness).

6.6. Premature Discontinuation of Investigational Agent

Study therapy may be prematurely discontinued for any participant for any of the following reasons:

1. Evidence of infection either cutaneously, or systemically.
2. Severe worsening of AD which in the opinion of the investigator requires stopping of the medication.
3. Evidence of contact allergy to investigative medication.
4. Evidence of non-compliance to study protocol that in the opinion of the investigator requires discontinuation of investigational agent.
5. Study therapy may also be prematurely discontinued for any participant if the investigator believes that the study treatment is no longer in the best interest of the participant.

7. Other Medications

7.1. Concomitant Medications

7.1.1. Protocol-mandated

At the start of the study, eligible subjects will receive Dove soap as well as Cetaphil moisturizing lotion to use throughout the duration of the study.

7.2. Prohibited Medications

1. Use of any topical AD treatments (including topical steroids and topical calcineurin inhibitors) to either arm within one week of the Treatment visit
2. Use of antihistamines within 7 days of the Treatment Visit
3. Use of any systemic AD therapies or any systemic immunosuppressive therapy (steroids, CsA, MTX, etc.) within 28 days of the Treatment visit
4. Use of any oral or topical antibiotics for up to four weeks prior to the Treatment Visit
5. Use of bleach baths within 7 days of the Treatment Visit

7.3. Rescue Medications

If infection occurs, the treatment will include topical and/or oral antibiotics, depending on the severity of the infection clinically, and Cetaphil® moisturizing lotion (for irritation and dryness). The topical antibiotic of choice will be mupirocin. The oral antibiotic of choice will depend on the individual subject's medical history, including any possible contraindications to certain medications due to allergies or other concomitant medication use, but doxycycline will be the first line oral antibiotic, followed by a cephalosporin or penicillinase-resistant penicillin.

8. Study Procedures

8.1. Enrollment

The research study will be explained in lay terms to each potential research participant. The potential participant will sign an informed consent form before undergoing any study procedures. Once the informed consent has been signed, and meets all the inclusion and exclusion criteria, the participant is considered enrolled in the study and will be assigned a unique participant number.

8.2. Screening/Baseline Visit

The purpose of the screening period is to confirm eligibility to continue in the study.

1. The following procedures, assessments, and laboratory measures will be conducted to determine participant eligibility: Prior to beginning any study procedures, subjects will first be asked to review and sign the informed consent form.
2. After obtaining informed consent, the inclusion/exclusion criteria will be reviewed.
3. A brief medical history and physical exam/vital signs will be performed to assess whether the subject meets the required criteria for the study.
4. Female subjects of child-bearing potential will complete a urine pregnancy test while in the office to ensure that they are not pregnant.

[figure not shown]
5. Patients who meet the inclusion and exclusion criteria will then have their lesional AD skin scored according to the localized SCORAD grading scale, and the extent of AD lesional skin on their bilateral arms will be recorded.
6. A skin swab performed on the lesional atopic dermatitis skin of their antecubital fossae, will be performed to detect the presence of *S. aureus*.

Subjects who do not meet the inclusion/exclusion criteria due to the application or use of prohibited medications within the timeframe noted will be considered screen-failures. Skin swabs of these patients will not be performed. These subjects may return for another screening visit after completing the necessary wash-out period (7 days for topical medications, 28 days for oral medications) if they are interested in doing so. Subjects eligible for this study will be randomized at the Treatment visit 1 to either AMT cream or placebo in a 2:1 allocation ratio (AMT cream: placebo).

8.3. Study Visits or Study Assessments

Aim: To determine the change in abundance of *Staph aureus* from baseline after 1 week BID application of AMT.

The study flowchart is provided below:

This experiment will consist of up to 9 office visits (Screening, Treatment, 2 optional visits, and 5 Follow-up visits) and two phone calls. All office visits will occur at the UCSD Dermatology Clinic. Up to twenty seven (27) subjects with AD will be recruited for this study. The exact study procedures are noted below:

Screening Visit 1 (Day -60 to Day -2)

Prior to beginning any study procedures, subjects will first be asked to review and sign the informed consent form. After obtaining informed consent, the inclusion/exclusion criteria will be reviewed. A brief medical history, vital signs, and physical exam will be performed in helping to assess whether the subject meets the required criteria for the study. Female subjects of child-bearing potential will complete a urine pregnancy test while in our office to ensure that they are not pregnant. Patients who meet the inclusion and exclusion criteria

will then have their lesional AD skin scored according to the SCORAD grading scale, EASI, and modified EASI, and localized SCORAD, and the extent of AD lesional skin on their bilateral arms will be recorded. A skin swab will be performed on the lesional atopic dermatitis skin of their antecubital fossae bilaterally to detect the presence of *S. aureus*. Additionally, we will take four (4) culture swabs from the subject's non-lesional (no AD) skin on their upper arms. These culture swabs will be placed in tryptic soy broth (TSB) until processed in the lab, where they will be used to grow the subject's antimicrobial peptide-producing *Staph* species to use for the autologous microbiome transplant. Subjects will then receive a bar of Dove moisturizing soap, which they will be instructed to use whenever they shower until after the follow-up visit is complete. This will conclude the screening visit. The total time for this visit will be approximately 40 minutes.

Subjects who do not meet inclusion and exclusion criteria due to their concomitant medications will be asked whether they would be willing to washout of their medications prior to Visit 3 should they have both *S. aureus* and *CoNS* colonization or for a repeat culture visit (if negative for *S. aureus* or *CoNS*). Subjects who agree to the washout will have swabs collected for assessment of *S. aureus* and *CoNS* colonization. Subjects who do not wish to washout out of the prohibited medications will be identified as screen failures and will not continue in the study.

Visit 2, Phone 1 (Day -59 to Day -1)

Subjects will be notified via telephone whether or not their skin swab grew *S. aureus* and whether they have antimicrobial *Staphylococcus* species present. Subjects with a skin culture positive for *S. aureus* and antimicrobial coagulase-negative *Staph* (*CoNS*) will be enrolled in the study and visit 3 (Treatment visit) will be scheduled. For these subjects, they will be reminded to withhold their medications prior to Visit 3 according to protocol. Subjects with a negative *S. aureus* skin culture and/or are negative for *CoNS*, will be asked to withhold their medications according to the protocol (7 days for AD topical medication and antihistamines, and 28 days for oral AD medications), and a repeat screening visit will be scheduled for additional skin culture swabs. The total phone conversation should take approximately 5 minutes.

Repeat culture visit, as necessary (Day -31 to -2)

The purpose of the Repeat Culture Visit is to repeat skin swabbing to assess for the presence of *S. aureus* and *CoNS* following their medication washout (28 days for oral AD medications, 7 days for topicals and antihistamines). This visit will only be required for subjects who had negative cultures for *S. aureus* and/or *CoNS* and agree to washout of their medications for repeat swabbing.

Inclusion and exclusion criteria will be reviewed. Interim medical history and a physical exam will be performed. Female subjects of child-bearing potential will complete a urine pregnancy test while in our office to

ensure that they are not pregnant. Vital signs will be taken. Two (2) skin culture swabs total will be taken of their lesional antecubital fossae to assess for *S. aureus*. Additionally, four (4) skin culture swabs will be taken of their non-lesional skin to assess for antimicrobial *CoNS*. These culture swabs will be placed in tryptic soy broth (TSB) until processed in the lab, where they will be used to grow the subject's antimicrobial peptide-producing *Staph* species to use for the autologous microbiome transplant. This will conclude the repeat culture visit. The total time for this visit will be approximately 20 minutes.

Repeat phone call, as necessary (Day -30 to -1)

Subjects will be notified via telephone whether or not their skin swabs grew *S. aureus* and whether they have antimicrobial *Staphylococcus* species present. Subjects with a skin culture positive for *S. aureus* and antimicrobial coagulase-negative *Staph* (*CoNS*) will be enrolled in the study. For these subjects, Visit 3 (Treatment visit) will be scheduled. Subjects with a negative *S. aureus* skin culture or are negative for *CoNS* will be identified as screen failures.

Visit 3, Treatment Visit (Day 0)

Eligible subjects with + *S. aureus* and *CoNS* screening cultures will be enrolled in the study and instructed to return to the clinic. This waiting period will allow laboratory staff to grow and prepare the subject's endogenous AMP-producing bacteria to be mixed with Cetaphil for application at the treatment visit. A laboratory staff member will serve as an unblinded pharmacist and once eligibility information is relayed to the unblinded pharmacist, the subject will be randomized to an allocation ratio of 2:1 (AMT cream: vehicle cream). The subject will be asked not to bathe, shower, or exercise on the day of the treatment visit, and also that the application of any topical products to their arms on this day is prohibited. Hand washing is allowed, but subjects will be instructed to take care not to apply soap or water above their wrists.

This visit will begin by reviewing the subject's interim medical history, including medication history to ensure that he/she did not use any topical AD treatments on their arms or antihistamines within 7 days or oral AD treatments within 28 days of this visit. For all subjects, a focused physical exam will then be performed of the subject's bilateral arms to ensure that there is no evidence of cracks, breaks or infections of the skin on the arms. Vital signs will be taken. The localized SCORAD, modified EASI, global EASI and SCORAD grading scale will be used to rate the severity of the lesional AD skin on the subject's bilateral arms, and the extent of lesional AD skin on each arm will be recorded. Digital photographs of the lesional skin on both arms will be taken. Each photograph will also include a ruler so the scale of the lesions can be determined, as well as a card with the subject's identification number, visit date, and photograph location so that the photographs can be

identified when uploaded. Next, up to 3 skin swabs will be performed on each arm in a region of eczematous skin and non-lesional skin, for a total of up to 12 swabs. For the skin swabs, one culture swab and one to two DNA swabs will be taken from the eczematous skin from each arm, and one culture swab and one to two DNA swabs will be taken from the non-lesional skin on each upper inner arm for a total of up to twelve (12) swabs. After swabbing, the swabs are placed into either an empty Eppendorf tube (if analyzing the DNA of the bacteria present on the skin surface) or into a liquid medium such as tryptic soy broth (if analyzing the amount of bacteria present on the swabbed skin surface). These swabs will be analyzed in the lab to determine how many and what type of bacteria are present. The AMT cream or vehicle cream will then be applied to both arms by the gloved hands of a study coordinator. The moisturizers will be provided by [name] laboratory and will be in identical containers labeled either A or B. Neither the study coordinator nor the subject will know which cream is in which container. Container A or B will contain either Cetaphil alone or Cetaphil plus colonies of the subject's endogenous AMP-producing Staph grown in the lab from the subject's screening swab. A thin coat of cream A or B will be applied to both arms (excluding hand) in order to demonstrate proper application. Up to twelve (12) skin swabs will then be performed on both arms in the areas of cream application on lesional and non-lesional skin, between 5 minutes to an hour after cream application, depending on the discretion of the investigator. Following the skin swabs, the Cetaphil alone or Cetaphil with AMP-producing Staph will be reapplied onto the subjects' arms as previously described. The subject will be instructed to withhold use of any topical or oral AD medications until after their last in-clinic follow-up visit (Visit 8). The subject will be provided with aliquots of either the transplant or vehicle creams, enough for at least 4 days of application. Subjects will be instructed to apply the cream twice a day for the next 4 days, and will be instructed to apply the provided cream from one aliquot per arm. To minimize cross contamination, we will instruct subjects to wear long sleeve clothes and change into clean clothes every day. All creams should be stored at room temperature. Subjects will be reminded to use Dove soap provided to them, whenever they shower, but to avoid the upper extremities, until after their last in-clinic visit on Day 11 is complete. Subjects will be instructed to continue their daily skin care routine, and discouraged from using antibacterial soaps and swimming in the ocean or pool until their last in-clinic follow-up visit. They will also be instructed that if these events occur, to please notify the study staff at their next visit. At the end of the visit, subjects will be given an instruction sheet and a subject diary to assess for cream application appliance. They will be asked to bring the diary pages to their Follow-up Visit 4. This will conclude the treatment visit. We expect this visit to take approximately 20 minutes.

Optional Visit 1 (1 hour after cream application +/- 2 hours): Subjects will have the option to return to clinic for an optional visit approximately 1 hour after AMT cream application. At this optional visit, up to 12 skin swabs will be taken of the lesional and non-lesional skin on the arms (one culture swab and one to two DNA swabs for lesional and non-lesional skin of each arm). This visit will take approximately 15 minutes.

Optional Visit 2 (4 hours after cream application +/- 2 hours): Subjects will have the option to return to clinic for an optional visit approximately 4 hours after AMT cream application. At this optional visit, up to 12 skin swabs will be taken of the lesional arms and non-lesional skin on the arms (one culture swab and one to two DNA swabs for lesional and non-lesional skin of each arm). This visit will take approximately 15 minutes.

Visit 4 (Day 4 +/- 5): Subjects will return to the clinic to pick up fresh aliquots of the AMT or vehicle creams, and to return approximately 4 hours after last cream application. Any adverse events will be recorded. Subjects will be asked to refrain from bathing, exercising, or showering starting at 12:01am of Visit 4. Vital signs will be taken. Subject diaries will be collected at this time and a new subject diary will be dispensed to assess for cream application appliance. Used aliquots of cream will be collected at this visit. The localized SCORAD, modified EASI, global EASI and SCORAD grading scale will be used to rate the severity of the lesional AD skin on the subject's bilateral arms, and the extent of lesional AD skin on each arm will be recorded. Digital photographs of the lesional skin on both arms will be taken. Each photograph will also include a ruler so the scale of the lesions can be determined, as well as a card with the subject's identification number, visit date, and photograph location so that the photographs can be identified when uploaded. Next, one culture swab and one to two DNA swabs will be taken from the eczematous skin from each arm, and one culture swab and one to two DNA swabs will be taken from the non-lesional skin on each upper inner arm for a total of up to twelve (12) swabs. We expect this visit to take approximately 15 minutes.

Visit 5 (Day 7 +/- 7): Subjects will be asked to return to the clinic for Visit 5 approximately 4 hours after last cream application. Subject diaries will be collected at this time. Any used and unused aliquots of cream will be collected at this visit. Subjects will be asked to refrain from bathing, exercising, or showering starting at 12:01am of Visit 5. Vital signs will be taken. Any adverse events since the last visit will be recorded. A brief exam of the skin on subjects' arms will be performed. The severity of AD on each arm will be graded using the localized SCORAD, modified EASI and global SCORAD and EASI grading. Subjects will also be asked to grade their pruritus on a scale of 1-10, with 10 being the worst pruritus of their life. Digital photographs of the lesional skin on both arms will be taken. Next, one culture swab and one to two DNA swabs will be taken from the eczematous skin from each arm, and one culture swab and one to two DNA swabs will be taken from the non-lesional skin on each upper inner arm for a total of up to twelve (12) swabs to determine the microbial diversity and abundance. We expect this visit to take approximately 15 minutes.

Visit 6 (Day 8 +/- 7): Subjects will be asked to return to the clinic for follow-up. Any adverse events since the last visit will be recorded. A brief exam of the skin on subjects' arms will be performed. Subjects will be asked to refrain from bathing, exercising, or showering starting at 12:01am of Visit 6. Vital signs will be taken. The severity of AD on each arm will be graded using the localized SCORAD, modified EASI, and global SCORAD and EASI grading. Subjects will also be asked to grade their pruritus on a scale of 1-10, with 10 being the worst pruritus of their life. Digital photographs of the lesional skin on both arms will be taken. Next, one culture swab and one to two DNA swabs will be taken from the eczematous skin from each arm, and one culture swab and one to two DNA swabs will be taken from the non-lesional skin on each upper inner arm for a total of up to twelve (12) swabs. Any used cream will be collected. We expect this visit to take approximately 15 minutes.

